### 5.7.3 Electrocardiogram (ECG) Evaluations

Ventricular rate (bpm), PR interval (ms), QRS duration (ms), QT interval (ms), RR interval (ms), and QTcF (ms) interval will be evaluated at baseline, baseline 2h post-dose, week 1, week 2, week 4, week 8 and week 12.

A summary of abnormal clinically significant and not clinically significant electrocardiogram (ECG) results will be presented by treatment and visit. All ECG tests and results will be listed.

If multiple ECG evaluations were performed at baseline, the latest non-missing measurement prior to the first administration of study treatment will be used for the baseline value. For multiple ECG evaluations at post-baseline visits occurring during the same visit window, the closets measurement to

the actual visit date will be used for the analyses and summary tables. When two measurements are exactly equidistant to the exact visit date, the later will be used for the analyses and summary tables.

QT corrected using Fridericia formula is defined as :

$$QTcF(ms) = QT(ms) \times \sqrt[3]{\frac{HR(bpm)}{60}}$$

Values by visit from baseline and changes from baseline by post-baseline visit for PR interval, QRS duration, QT interval and QTcF interval will be summarised on overall subjects receiving VIT-2763, subjects receiving VIT-2763 by dose daily frequency and on subjects receiving placebo.

Shift tables from baseline to maximal on treatment status (Normal/Abnormal/Missing) will be also provided.

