8.1.4 Electrocardiogram

Computerised single 12-lead ECG recordings will have to be obtained locally according to Table 1. Each lead shall be recorded for at least 3 beats at a speed of 25 mm/s.

The following parameters will be recorded: ventricular rate, PR interval, QRS duration, QT interval and QTcF. These parameters plus the judgement by the physician will be entered in the eCRF. Print-outs of ECGs will have to be signed, dated and filed at the site.

At baseline, the Investigator must document clinically relevant ECG findings on the appropriate baseline eCRF pages and in the subject's hospital records. Any new clinically relevant ECG finding or aggravation/worsening of an already existing finding as assessed by the Investigator, must be reported as an AE (see Section 10).

[figure not shown]
8.1.5 **Body Height, Weight**

Body height (in cm, without shoes) must be measured at the screening visit only. Body weight must be measured in underwear or light clothing without shoes. The same calibrated scale must be used throughout the trial. Any new clinically relevant change in body weight must be reported as an AE (see Section 10).

8.1.6 **Documentation of Concomitant Treatments**

All medications and treatments prescribed at the moment of informed consent must be documented on the appropriate eCRF pages. In addition, treatments prescribed up to at least 3 months prior to obtaining the informed consent must be documented on the appropriate eCRF pages, irrespective if the treatment is still ongoing at the time of screening. All changes to or addition of concomitant treatments as of informed consent must be recorded (including changes in dose, change in formulation, starting or stopping medications) in the

eCRF. If the indication for changing a subject's concomitant treatment constitutes a new medical condition or a worsening of an existing clinical condition which is considered by the Investigator as being clinically relevant, the indication must be documented as an AE (see Section 10).

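### The ECG shift table merges clinically significant and not clinically significant abnormalities, so worsening between the two shows as no change in that table; ventricular rate and RR also lack a change summary

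*SAP*

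**What the plan says.** SAP 5.7.3 plans four kinds of ECG output.

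- **By-visit categories:** "A summary of abnormal clinically significant and not clinically significant electrocardiogram (ECG) results will be presented by treatment and visit". The two kinds of abnormality are kept apart, but the counts are not crossed with the subject's baseline.
- **Shift table:** "Shift tables from baseline to maximal on treatment status (Normal/Abnormal/Missing) will be also provided". Here there is a single abnormal level, and the section does not define maximal.
- **Continuous summaries:** "Values by visit from baseline and changes from baseline by post-baseline visit for PR interval, QRS duration, QT interval and QTcF interval" are to be summarised for VIT-2763 overall, by dosing frequency, and for placebo. The opening sentence of the section also names ventricular rate and RR interval as evaluated at each visit, but neither is in this list.
- **Listing:** "All ECG tests and results will be listed".

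On data collection, Protocol 8.1.4 says of the ECG measurements: "These parameters plus the judgement by the physician will be entered in the eCRF". On reporting, it says: "Any new clinically relevant ECG finding or aggravation/worsening of an already existing finding as assessed by the Investigator, must be reported as an AE".

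**The concern.** The 12-lead ECG is a named component of the primary safety endpoint (Protocol 3.4.1, SAP 2.6.1). Protocol 7.1 recommends ECG monitoring on nonclinical grounds and urges caution with drugs that prolong PR, QRS or QT. No inferential tests are planned, so the descriptive displays are the whole analysis.

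A shift table exists to show who got worse relative to their own starting point. With one abnormal level it can do this only for subjects who enter with a normal tracing. Exclusion criterion 10 in Protocol 5.3 removes subjects with clinically important cardiac findings, so an abnormality present at entry is more likely to be NCS than CS (an inference, not a stated figure). NCS to CS is then the main route by which such a subject could worsen, and it is the step that the table does not show.

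Ventricular rate raises a smaller, related question. The QTcF formula in SAP 5.7.3 uses heart rate as its correction term, yet the change in rate at the ECG time point is not among the planned change summaries.

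**Working it through.** The plan states no figure on this point. The check is an enumeration of table cells and a comparison of measurement times.

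**1. What the shift table can distinguish.** Order the statuses Normal < NCS < CS. Three worsening moves are possible.

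| Move, baseline to worst on treatment | Cell with the SAP levels | Cell with three levels |
|---|---|---|
| Normal to NCS | Normal to Abnormal | own cell, off the diagonal |
| Normal to CS | Normal to Abnormal | own cell, off the diagonal |
| NCS to CS | Abnormal to Abnormal (no change) | own cell, off the diagonal |

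Leaving Missing aside, the SAP grid has 2 x 2 = 4 cells, of which 1 represents worsening. The three-level grid has 3 x 3 = 9 cells, of which 3 represent worsening. Under the SAP levels, one of the three moves is shown as unchanged and the other two share a cell. Maximal status reduces to whether the subject had any abnormal tracing on treatment.

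**2. Whether the finer data exist.** Protocol 8.1.4 has the physician's judgement entered in the eCRF, and the by-visit summary in SAP 5.7.3 already needs the CS/NCS split. The three-level table therefore needs no new data.

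**3. Whether another table gives the same cross-tabulation.**

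- The by-visit CS/NCS counts are marginal. They show how many tracings were CS at a visit, not whether those subjects began as Normal or NCS.
- The interval summaries describe changes in PR, QRS, QT and QTcF, not the overall reading.
- The adverse event tables in SAP 5.7.1 are by system organ class and preferred term, and are not crossed with baseline ECG status.
- The listing holds every result, but the reader would have to build the table from it.

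**4. How many subjects.** For an arm of n subjects, the expected number misdisplayed is n x p x q, where p is the proportion NCS at baseline and q is the probability that such a subject becomes CS on treatment. The documents give neither p nor q. If p is assumed to be 20%, 40% or 60%, an active arm of 8 adults has 8 x 0.2 = 1.6, 8 x 0.4 = 3.2 or 8 x 0.6 = 4.8 subjects who start NCS. A placebo arm of 4 has 0.8, 1.6 or 2.4. These are the subjects exposed to the problem; the number misdisplayed is that figure multiplied by the unknown q. The arm sizes follow from the 8:8:4 ratio and the minimum of 20 in Cohort I (Protocol 12.3), so they too are minima.

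**5. Ventricular rate and RR.**

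| Measurement | Timing on treatment | Change from baseline planned? |
|---|---|---|
| Pulse rate (vital signs) | before dosing, V3 to V8 (Protocol 8.1.3) | yes (SAP 5.7.4) |
| PR, QRS, QT, QTcF | 2-3 hours after the morning dose (Protocol Table 1 notes, 6.4.2.1) | yes (SAP 5.7.3) |
| Ventricular rate, RR | same ECG, 2-3 hours after the morning dose | not named |

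Phase 1 Tmax ranged from 0.50 to 3 hours (Protocol 1.2.3). The ECG is therefore taken within or close to the time of peak concentration, whereas pulse rate is taken at trough. SAP 5.7.3 gives QTcF = QT x (HR/60)^(1/3), so any divergence between the QT and QTcF changes comes from rate. The pulse-rate summary does not supply the rate change at that time. RR is not in the Protocol 8.1.4 list of recorded parameters, but it follows from rate as 60,000/rate in ms.

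**The case against.** The strongest reply is that nothing is lost from the report. Every ECG result is listed, and SAP 5.1.5 orders listings by cohort, treatment group, body weight and subject, so with arms of about 8, 8 and 4 adults a reader can follow each subject. Protocol 8.1.4 makes "aggravation/worsening of an already existing finding" reportable as an adverse event when the investigator so assesses it, and Protocol 10.5.6 does the same for any ECG abnormality judged clinically significant. A move from NCS to CS is therefore an adverse event by rule, and SAP 5.7.1 tabulates it by arm. Concern about PR, QRS or QT prolongation is quantitative and is met by the interval changes, whatever the baseline reading. Finally, Protocol 12.8.1 asks only for the interval summaries and a listing of abnormal findings; the shift table is an addition made by the SAP.

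Most of this stands, and it limits the point. A reader might infer that ECG worsening in subjects with an abnormal entry tracing would go unseen. The documents do not support that, because the listing, the by-visit counts and the adverse event tables each carry part of it. A reader might also take the 20% to 60% range above as the share of subjects misdisplayed. It is only an assumed share who could be affected.

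What remains is narrower. No other planned table crosses baseline status with worst on-treatment status. The adverse event route depends on the investigator having filed the event, so a shift table that keeps the CS level would be a useful check on it.

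On ventricular rate, it can be argued that SAP 5.7, through the standard statistics of SAP 5.1.1, already covers by-visit values. That is fair, but the explicit sentence on changes, "changes from baseline by post-baseline visit for PR interval, QRS duration, QT interval and QTcF interval will be summarised", leaves rate and RR out.

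**Conclusion.** The point holds for the shift table alone. As worded, the table shows NCS to CS as no change and cannot separate Normal to NCS from Normal to CS, although the distinction is collected and is used elsewhere in the same section. It is a weakness of descriptive reporting in a primary safety component. It touches no hypothesis, error rate or sample size, and it does not put the SAP below what the protocol requires.

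The number of subjects affected cannot be stated, since both the baseline abnormality rate and the NCS-to-CS rate are absent. For scale only, one such subject is 1/8 = 12.5% of an active arm at the minimum adult size. The conclusion assumes that the physician's judgement in the eCRF distinguishes CS from NCS, which the by-visit summary presupposes.

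The ventricular-rate omission holds in a smaller form: the change from baseline at the post-dose ECG is not planned, for rate or for RR, and the pre-dose pulse-rate summary does not replace it.

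**What to change.** In SAP 5.7.3:

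1. Replace the shift-table levels with Normal / Abnormal NCS / Abnormal CS / Missing. Define maximal on-treatment status as the worst in the order Normal < NCS < CS, and present the table by treatment group.
2. Add ventricular rate and RR interval to the parameters summarised as values and changes from baseline by visit.

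The cost is one more row and column in a table already planned, and two more parameters in another. No new assessment is needed: the readings and rates are already collected, and RR can be derived from rate where it is not recorded.

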#### 5.7.4 Vital Signs Evaluations

The values and change from baseline results of Systolic Blood Pressure (SBP) (mmHg), Diastolic Blood Pressure (DBP) (mmHg), pulse rate (bpm) and body weight (kg) will be summarised by visit split by treatment group.

For each vital signs variable, the Baseline value is defined as the last non-missing measurement collected/derived prior to the first study medication administration at Baseline visit.

Vital signs will be presented for individual subjects in data listings.

If multiple vital signs evaluations were performed at baseline, the latest non-missing measurement prior to the first administration of study treatment will be used for the baseline value. For multiple Vital signs evaluations at post-baseline visits occurring during the same visit window, the closest measurement to the actual visit date will be used for the analyses and summary tables. When two measurements are exactly equidistant to the exact visit date, the later will be used for the analyses and summary tables.

## 5.8 Physical Examinations

Physical examinations, including significant abnormalities, will be listed.

## 5.9 Other Analyses

#### 5.9.1 Iron Pharmacodynamics Analyses

The values and change from baseline results of iron pharmadynamic parameters (serum iron, serum ferritin, serum transferrin, unsaturated iron binding capacity, calculated transferrin saturation) will be summarized and listed by treatment group and timepoints. No formal statistical tests are planned.

For each iron pharmadynamic parameters, the Baseline value is defined as the last non-missing measurement collected/during screening period.

# 5.9.2 Pharmacokinetics Analyses

The Pharmacokinetic endpoint is the plasma concentrations of VIT-2763 on Baseline, Week4, Week 8 and Week 12.

The population pharmacokinetic analysis will be described in a separate analysis plan.

Pharmacokinetic plasma concentration of VIT-2763 will be summarized and listed by treatment group and timepoints using descriptive statistics (including arithmetic mean, SD, arithmetic CV%, median, observed maximum, minimum, N and for back-transformed data geometric mean and geometric SD). No formal statistical tests are planned.

The following rules will be applied if there are values that are below the limit of quantification (BLQ) or if there are missing values (eg, no result [NR]) in a plasma concentration data sets to be summarized.

- For the calculation of summary statistics, BLQ values will be set to zero.
- If an embedded BLQ value is considered anomalous within the concentration time profile, this
  value will be excluded from the summary statistics.
- Where there is NR, these will be set to missing.
- If values are obtained from more than or equal to 3 subjects by dose group, the summary statistics will be calculated.
- If values are obtained from less than 3 subjects by dose group, all arithmetic and geometric summary statistics will be denoted as NC (except min and max values).

## **APPENDICES**

## APPENDIX A: LABORATORY PARAMETERS

## Haematology parameters:

Test Description	Conventional Units	SI Units	Number of decimal places
Haemoglobin	g/dL	g/L	1
Fetal Haemoglobin,EDTAwb,335	%	%	1
Hematocrit	%		0
RBC	x10^6/uL	TI/L	1
Mean cell volume (MCV)	fL	fL	0
mean cell Hb (MCH)	pg	pg	0
mean cell Hb concentration (MCHC)	g/dL	g/L	0
Reticulocyte Count %-CL	%	%	1
Reticulocyte Count WBEDTA-CL	x10^6/uL	TI/L	3
red cell distribution width (RDW)	%	%	1

WBC	x10^3/uL	GI/L	2
Platelets	x10^3/uL	GI/L	0

# **Biochemistry parameters:**

Test Description	Conventional Units	SI Units	Number of decimal places
Serum Sodium	mEq/L	mmol/L	0
Serum Potassium	mEq/L	mmol/L	1
Magnesium	mg/dL	mmol/L	1
Calcium (EDTA)	mg/dL	mmol/L	1
Serum Chloride	mEq/L	mmol/L	0
Total Bilirubin	mg/dL	umol/L	1
Urea Nitrogen	mg/dL	mmol/L	0
Serum Uric Acid	mg/dL	umol/L	1
Creatinine(Rate Blanked)-2dp	mg/dL	umol/L	2
Total Protein	g/dL	g/L	1
Alkaline Phosphatase	U/L	U/L	0
AST (SGOT)	U/L	U/L	0
ALT (SGPT)	U/L	U/L	0
GGT	U/L	U/L	0
Glutamate Dehydrogenase-RUO	U/L	U/L	0
LDH	U/L	U/L	0
Haptoglobin	mg/dL	g/L	0
Serum Amylase	U/L	U/L	0
Serum Bicarbonate	mEq/L	mmol/L	1
eGFR (CKD-EPI GFR)	mL/min/1.73m 	mL/min/1.73m 	0
Unconjugated bilirubin (indirect bilirubin)	mg/dL	umol/L	0
Creatine Kinase	U/L	U/L	0
Folic acid (folate)	ng/mL	nmol/L	1
Vitamin B12	pg/mL	pmol/L	0
Albumin-BCG	g/dL	g/L	1

Serum Glucose	mg/dL	mmol/L	0
Cholesterol (High Performance)	mg/dL	mmol/L	0
Triglycerides (GPO)	mg/dL	mmol/L	0
Total Iron, Serum	ug/dL	umol/L	0
Ferritin	ng/mL	ug/L	1
Unsaturated Iron Binding Capacity	ug/dL	umol/L	0
Transferrin-CL	mg/dL	g/L	3

# Coagulation parameters:

Test Description	Conventional Units	SI Units	Number of decimal places
Prothrombin Time	sec	Sec	1
APTT-FSL	sec	Sec	1
Thrombin Time, Na Cit pl-CL	sec	sec	1
